APPENDIX D: CLINICAL LABORATORY ANALYTES

Clinical Chemistry Panel [1]

Alanine aminotransferase Albumin

Alkaline phosphatase Aspartate aminotransferase

Bicarbonate Blood urea nitrogen

Calcium Chloride

Creatine kinase Creatinine [2, 3]
Cystatin C [3] Direct bilirubin

Glucose Lactate dehydrogenase

Lipase Potassium
Sodium Total bilirubin

Total protein

- 1. Central or local laboratory results including those obtained as standard of care may be used to determine eligibility. Blood samples from Day 0 (pre-infusion baseline) and onward must be collected for analysis at the central laboratory.
- 2. For determination of study eligibility: creatinine clearance using the Cockcroft-Gault equation for adult participants, eGFR using the Schwartz equation for pediatric participants.
- 3. For the exploratory objective evaluating renal function over the 24-week study period, eGFR will be estimated using creatinine and cystatin C alone and in combination.

eGFR = estimated glomerular filtration rate.

Sources: Laskin BL, Denburg MR, Furth SL, et al. The natural history of BK polyomavirus and the host immune response after stem cell transplantation. *Clin Infect Dis.* 2019;pii:ciz1194. doi: 10.1093/cid/ciz1194. [Epub ahead of print] (see Reference 46); and Inker LA, Schmid CH, Tighiouart H, et al. Estimating glomerular filtration rate from serum creatinine and cystatin C. *N Engl J Med.* 2012 Jul 5;367(1):20-9.

Hematology (Central Laboratory)

Hematocrit Hemoglobin

Platelets Red blood cell count

White blood cell count and differential [1]

1. Manual microscopic review is performed only if white blood cell count and/or differential values are out of reference range.

Viral Load in Blood and Urine (Central Laboratory)

Adenovirus BK virus

Cytomegalovirus Epstein-Barr virus

Human herpesvirus 6 JC virus

Note: When viral load determination is performed in the laboratory, residual viral DNA will be stored for potential viral sequencing and genotyping in the event of recurrent infection.

Note: Viral load determination at screening may be performed at a local or central laboratory for the purpose of determining eligibility. Blood and urine from Day 0 (pre-infusion baseline) and onward must be collected for viral load analysis at the central laboratory. Additional post-infusion samples may be collected, as clinically indicated.

DNA = deoxyribonucleic acid.

Urinalysis

Blood (if positive, reflex to microscopy)

Leukocyte esterase

Stool Specimen (Central Laboratory)

Adenovirus Cytomegalovirus

Note: If a stool specimen is clinically indicated, stool samples will also be sent to the central laboratory for research purposes.

Cerebrospinal Fluid Sample (Central Laboratory)

Cytomegalovirus

Human herpesvirus 6

JC virus

Note: If a cerebrospinal fluid sample is clinically indicated, samples will also be sent to the central laboratory for research purposes. Cerebrospinal fluid samples required for clinical care of the participant take precedence over these research-related evaluations.

Other Laboratory Assessments

Serum pregnancy test [1]

Follicle-stimulating hormone [2]

Peripheral blood mononuclear cells (PBMCs) and plasma [3]

- 1. For participants of childbearing potential only. A serum (human chorionic gonadotropin) pregnancy test will be performed at screening. A urine or serum pregnancy test must be performed <24 hours before each infusion and at the end of study visit for participants of childbearing potential. A negative result must be confirmed prior to administration of each infusion. These tests may be performed at the local laboratory.
- 2. Follicle-stimulating hormone will be tested at screening for women of nonchildbearing potential who are postmenopausal, defined as 12 consecutive months with no menses without an alternative medical cause.
- 3. At each time point indicated in Appendix A, blood will be collected into a cell separation tube and processed to generate a PBMC fraction and a plasma fraction. Human genetic DNA will be extracted from the PBMC fraction. The DNA from PBMC and plasma fractions will be cryopreserved for potential future evaluation of virus-specific T cell persistence (PBMC fraction) and for future evaluation of cytokines and/or other humoral markers of inflammation/immune function (plasma fraction).

DNA = deoxyribonucleic acid; PBMC = peripheral blood mononuclear cell.

APPENDIX E: GRAFT VERSUS HOST DISEASE SCALES

MAGIC Criteria for Staging and Grading of Acute Graft Versus Host Disease

	Skin	Liver		Lower GI
Stage	(Active Erythema Only)	(Bilirubin)	Upper GI	(Stool Output/Day)
				Adult: <500 mL/day or
			No or intermittent	<3 episodes/day.
	No active (erythematous)		nausea, vomiting,	Child: <10 mL/kg per day or
0	GVHD rash	<2 mg/dL	or anorexia	<4 episodes/day.
				Adult: 500-999 mL/day or
			Persistent nausea,	3-4 episodes/day.
	Maculopapular rash		vomiting, or	Child: 10-19.9 mL/kg per day
1	<25% BSA	2-3 mg/dL	anorexia	or 4-6 episodes/day.
				Adult: 1000-1500 mL/day or
				5-7 episodes/day.
	Maculopapular rash			Child: 20-30 mL/kg per day or
2	25%-50% BSA	3.1-6 mg/dL	-	7-10 episodes/day.
				Adult: >1500 mL/day or
				>7 episodes/day.
	Maculopapular rash			Child: >30 mL/kg per day or
3	>50% BSA	6.1-15 mg/dL	-	>10 episodes/day.
	Generalized erythroderma			Severe abdominal pain with or
	(>50% BSA) plus bullous			without ileus or grossly bloody
	formation and desquamation			stool (regardless of stool
4	>5% BSA	>15 mg/dL	=	volume).

Note: Overall clinical grade (based on most severe target organ involvement):

Grade 0: No Stage 1 to 4 of any organ.

Grade I: Stage 1 to 2 skin without liver, upper GI, or lower GI involvement.

Grade II: Stage 3 rash and/or Stage 1 liver and/or Stage 1 upper GI and/or Stage 1 lower GI.

Grade III: Stage 2 to 3 liver and/or Stage 2 to 3 lower GI, with Stage 0 to 3 skin and/or Stage 0 to 1 upper GI.

Grade IV: Stage 4 skin, liver, or lower GI involvement, with Stage 0 to 1 upper GI.

BSA = body surface area; GI = gastrointestinal; GVHD = graft versus host disease.

Source: Harris AC, Young R, Devine S, et al. International, multicenter standardization of acute graft-versus-host disease clinical data collection: a report from the Mount Sinai Acute GVHD International Consortium. *Biol Blood Marrow Transplant*. 2016;22(1):4-10.

Response Definitions for Acute Graft Versus Host Disease

Response Term	Definition
	Complete resolution of all signs and symptoms of GVHD in all organs without
CR	intervening salvage therapies.
	Improvement of 1 stage in 1 or more organs involved by GVHD without progression
PR	in others.
	Improvement in at least 1 involved organ with progression or newly developed
Mixed response	GVHD in 1 or more organs.
	Worsening in 1 or more organs by 1 or more stage without improvement in any
Progression	involved organ.
NR	No improvement or deterioration in any organ within 14 days of therapy initiation.

CR = complete response; GVHD = graft versus host disease; NR = no response; PR = partial response.

Source: Center for International Blood & Marrow Transplant Research (CIBMTR). Clinical trial endpoints for participants with acute GVHD. May 2009.

https://www.cibmtr.org/Meetings/Materials/GVHDworkshop/GvHD%20Workshop%20Library/08_Alousi_FDAaGVHDwrkshpMay09.pdf. Accessed 09 Nov 2020.

National Institutes of Health Global Severity of Chronic Graft Versus Host Disease

Mild Chronic GVHD	Moderate Chronic GVHD	Severe Chronic GVHD
	3 or more organs involved with no	
	more than score 1 or at least	
1 or 2 organs involved with no	1 organ (not lung) with a score of 2	At least 1 organ with a score of 3 or
more than score 1 plus lung score 0	or lung score 1	lung score of 2 or 3

Note: Key points:

In skin: higher of the 2 scores to be used for calculating global severity.

In lung: FEV1 is used instead of clinical score for calculating global severity.

If the entire abnormality in an organ is noted to be unequivocally explained by a non-GVHD documented cause, that organ is not included for calculation of the global severity.

If the abnormality in an organ is attributed to multifactorial causes (GVHD plus other causes), the scored organ will be used for calculation of the global severity regardless of the contributing causes (no downgrading of organ severity score).

GVHD = graft versus host disease.

Source: Jagasia MH, Greinix HT, Arora M, et al. National Institutes of Health Consensus Development Project on Criteria for Clinical Trials in Chronic Graft-Versus-Host-Disease: I. The 2014 Diagnosis and Staging Working Group Report. *Biol Blood Marrow Transplant*. 2015;21:389-401.e1.

National Institutes of Health Response Determinations for Chronic Graft Versus Host Disease

Organ	Complete Response	Partial Response	Progression
	NIH Skin Score 0 after	Decrease in NIH Skin Score	Increase in NIH Skin Score by
Skin	previous involvement	by 1 or more points	1 or more points, except 0 to 1
	NIH Eye Score 0 after	Decrease in NIH Eye Score	Increase in NIH Eye Score by
Eyes	previous involvement	by 1 or more points	1 or more points, except 0 to 1
	NIH Modified Oral Mucosa	Decrease in NIH Modified	Increase in NIH Modified
	Rating Score 0 after previous	Oral Mucosa Rating Score of	Oral Mucosa Rating Score of
Mouth	involvement	2 or more points	2 or more points
			Increase in NIH Esophagus
	NIH Esophagus Score 0 after	Decrease in NIH Esophagus	Score by 1 or more points,
Esophagus	previous involvement	Score by 1 or more points	except 0 to 1
			Increase in NIH Upper GI
	NIH Upper GI Score 0 after	Decrease in NIH Upper GI	Score by 1 or more points,
Upper GI	previous involvement	Score by 1 or more points	except 0 to 1
			Increase in NIH Lower GI
	NIH Lower GI Score 0 after	Decrease in NIH Lower GI	Score by 1 or more points,
Lower GI	previous involvement	Score by 1 or more points	except from 0 to 1
	Normal ALT, alkaline		
	phosphatase, and total		
	bilirubin after previous		
Liver	elevation of 1 or more	Decrease by 50%	Increase by 2×ULN
		Increase by 10% predicted	Decrease by 10% predicted
	Normal %FEV1 after	absolute value of %FEV1	absolute value of %FEV1
	previous involvement		
		If PFTs not available,	If PFTs not available, increase
	If PFTs not available, NIH	decrease in NIH Lung	in NIH Lung Symptom Score
-	Lung Symptom Score 0 after	Symptom Score by 1 or more	by 1 or more points, except 0
Lungs	previous involvement	points	to 1
	Both NIH Joint and Fascia	Decrease in NIH Joint and	Increase in NIH Joint and
Talinda and	Score 0 and P-ROM score 25	Fascia Score by 1 or more	Fascia Score by 1 or more
Joints and	after previous involvement by	points or increase in P-ROM	points or decrease in P-ROM
fascia	at least 1 measure	score by 1 point for any site	score by 1 point for any site
	Clinician consult consult	Clinician overall severity	Clinician overall severity
C1-1-1	Clinician overall severity	score decreases by 2 or more	score increases by 2 or more
Global	score 0	points on a 0-10 scale	points on a 0-10 scale

%FEV1 = percent predicted forced expiratory volume in the first second; ALT = alanine aminotransferase; GI = gastrointestinal; NIH = National Institutes of Health; PFT = pulmonary function test; P-ROM = photographic range of motion; ULN = upper limit of normal.

Source: Lee ST, Wolff D, Kitko C, et al. Measuring therapeutic response in chronic graft-versus-host disease. *Biol Blood Marrow Transplant*. 2015;21(6):984-999.

APPENDIX F: CYTOKINE RELEASE SYNDROME SCALE

For participants who have a presumptive diagnosis of cytokine release syndrome (CRS) based on the clinical judgement of the Investigator, the CRS should be graded according to the American Society for Transplantation and Cellular Therapy (ASTCT) consensus grading for CRS shown in the table below rather than by CTCAE. The ASTCT consensus grading was developed for chimeric antigen receptor (CAR)-T cell therapies in which sustained engagement between CAR-T cells and targeted malignant cells is expected, leading to substantial rates of CRS. By contrast, CRS remains only a theoretical concern for virus-specific T cells.

CRS is defined as a supraphysiologic response following any immune therapy that results in the activation or engagement of endogenous or infused T cells and/or other immune effector cells. Symptoms can be progressive, must include fever at the onset, and may include hypotension, capillary leak (hypoxia), and end organ dysfunction. (For additional details, see Appendix G below.)

Symptoms of Cytokine Release Syndrome by Grade

Symptoms of Cytokine Release Syndrome by Grade				
Grade	1	2	3	4
CRS Parameter				
Fever [a]	≥38.0°C	≥38.0°C	≥38.0°C	≥38.0°C
		With	l .	
			Requiring vasopressors	Requiring multiple
		Not requiring	with or without	vasopressors (excluding
Hypotension	None	vasopressors.	vasopressin.	vasopressin).
		And/or	[b]	
			Requiring high-flow	
		Requiring low-flow	nasal cannula (oxygen	
		nasal cannula	delivered at	Requiring positive
		(oxygen delivered at	>6 L/minute), facemask,	pressure (eg, CPAP,
		≤6 L/minute) or	nonrebreather mask, or	BiPAP, intubation,
Hypoxia	None	blow-by.	Venturi mask.	mechanical ventilation).

Note: Organ toxicities associated with CRS may be graded according to CTCAE v5.0 but they do not influence CRS grading. Note: Grade 5 CRS is defined as death due to CRS in which another cause is not the principal factor leading to the outcome.

BiPAP = bilevel positive airway pressure; CPAP = continuous positive airway pressure; CRS = cytokine release syndrome; CTCAE = Common Terminology Criteria for Adverse Events.

Source: Lee DW, Santomasso BD, Locke FL, et al. ASTCT consensus grading for cytokine release syndrome and neurologic toxicity associated with immune effector cells. *Biol Blood Marrow Transplant*. 2019;25(4):625-638.

a. Fever is defined as temperature ≥38.0°C not attributable to any other cause. In participants who have CRS and then receive antipyretic or anticytokine therapy such as tocilizumab or steroids, fever is no longer required to grade subsequent CRS severity. In this case, CRS grading is driven by hypotension and/or hypoxia.

b. CRS grade is determined by the more severe event: hypotension or hypoxia not attributable to any other cause. For example, a participant with temperature of 39.5°C, hypotension requiring 1 vasopressor, and hypoxia requiring low-flow nasal cannula is classified as grade 3 CRS.

APPENDIX G: MONITORING FOR AND MANAGEMENT OF CYTOKINE RELEASE SYNDROME

The following recommendations have been adapted from recommendations for patients receiving chimeric antigen receptor (CAR)-T cells who develop cytokine release syndrome (CRS). CRS is common following CAR-T cell therapy, but remains a theoretical concern following infusion of virus-specific T cells (VSTs). No cases of CRS were observed in 58 participants in the phase 2 CHARMS study of VSTs for viral infections following allogeneic hematopoietic cell transplant (HCT). Nevertheless, Investigators should remain vigilant for the signs and symptoms of CRS, particularly during the first four weeks following VST infusion, and should be prepared to treat participants immediately for CRS should it develop. Investigators should also counsel participants to seek immediate medical attention if they develop concerning clinical findings. At the first sign of CRS, immediately evaluate the participant for hospitalization and institute treatment as outlined below or according to treatment protocols in use at the study site. CRS typically begins within 1 to 14 days (median 2 to 3 days) after CAR-T cell therapy.

It is also important to note that the common symptoms of CRS are not unique to CRS and clinicians must be cautious and exclude other causes of fever, hypotension, hemodynamic instability, and/or respiratory distress, such as an overwhelming infection.⁴

Treatment of Cytokine Release Syndrome

CRS Grade	CRS Severity	Management
1	Prodromal syndrome: Low-grade fever, fatigue, anorexia	Observe in person; exclude infection; administer antibiotics per local guidelines if neutropenic; provide symptomatic support.
2	CRS requiring mild intervention (≥1 of the following): • High fever • Hypoxia • Mild hypotension	Administer antipyretics, oxygen, intravenous fluids and/or low-dose vasopressors as needed.
3 to 4	CRS requiring moderate to aggressive intervention (≥1 of the following): • Hemodynamic instability despite intravenous (IV) fluids and vasopressor support • Worsening respiratory distress, including pulmonary infiltrates increasing oxygen requirement including high-flow oxygen and/or need for mechanical ventilation • Rapid clinical deterioration	Administer high-dose and/or multiple vasopressors, oxygen, mechanical ventilation and/or other supportive care as needed. Administer tocilizumab: • Patient weight <30 kg: 12 mg/kg IV over 1 hour • Patient weight ≥30 kg: 8 mg/kg IV over 1 hour (maximum dose 800 mg) If there is no clinical improvement, repeat tocilizumab after a minimum interval of 8 hours. If there is no response to a second dose of tocilizumab, consider a third dose of tocilizumab or pursue alternative measures for treatment of CRS. Limit to a maximum total of 4 doses of tocilizumab. If there is no clinical improvement within 12 to 18 hours of the first tocilizumab dose, or if there is worsening at any time, administer methylprednisolone 2 mg/kg IV as an initial dose, then 2 mg/kg IV per day until vasopressors and high-flow oxygen are no longer needed, then taper.

CRS = cytokine release syndrome; IV = intravenous.

References:

- 1. KYMRIAH® (tisagenlecleucel) suspension for intravenous infusion, prescribing information. https://www.novartis.us/sites/www.novartis.us/files/kymriah.pdf. Accessed on 09 Nov 2020.
- 3. Porter DL and Maloney DG. Cytokine release syndrome (CRS). Post TW, ed. UpToDate. Waltham, MA. Updated 06 Apr 2020. https://www.uptodate.com/contents/cytokine-release-syndrome-crs. Accessed on 09 Nov 2020.

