4.3.2 Discontinuation of Study Treatment

The following do not fulfill any of the criteria for withdrawal from the study but do make the participant ineligible to receive any additional infusions of study treatment:

• Development of irreversible, life-threatening, Grade 3 to 4 acute GVHD or a Grade 3 to 4 non-hematologic adverse event between the first and second doses of PSL or placebo that is

considered related to study treatment administration. If this occurs, the participant's toxicities will be followed until resolution or until the participant's participation in the study ends.

- Receipt of any other hematopoietic stem cell product.
- Receipt of therapy for relapse of the participant's primary malignancy.
- Occurrence of Grade 3 or 4 CRS that persists beyond 72 hours. If this occurs, the participant's toxicities will be followed until resolution or until the participant's participation in the study ends.
- Pregnancy.

If any of the above criteria are met, every effort should be made to keep the participant in the study and continue follow-up.

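### Appendix G's CRS management table reuses the Appendix F grade numbers with different descriptions, so one patient can be directed to two different management rows

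*Protocol*

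**What the plan says.** Appendix F of the protocol states that "the CRS should be graded according to the American Society for Transplantation and Cellular Therapy (ASTCT) consensus grading for CRS shown in the table below". In that table every grade column carries the same fever threshold, and footnote a says "Fever is defined as temperature ≥38.0°C not attributable to any other cause". Hypotension and hypoxia are what move the grade above 1. Footnote b gives a worked case: "a participant with temperature of 39.5°C, hypotension requiring 1 vasopressor, and hypoxia requiring low-flow nasal cannula is classified as grade 3 CRS".

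Appendix G follows with a management table whose first column is also headed as the CRS grade. Grade 1 is a prodrome with low-grade fever. Grade 2 needs any one of high fever, hypoxia or mild hypotension, and its management entry includes "oxygen, intravenous fluids and/or low-dose vasopressors as needed". Grades 3 and 4 share one row. Its haemodynamic criterion is instability that continues despite IV fluids and vasopressors; worsening respiratory distress and rapid deterioration are the alternatives.

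The grade is used elsewhere. Section 4.3.2 makes a participant ineligible for further infusions on "Occurrence of Grade 3 or 4 CRS that persists beyond 72 hours". The incidence and severity of CRS is a secondary safety endpoint (Protocol Section 8).

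On which scale to record, Protocol Sections 8 and 8.1.4 and SAP Section 2.3.4 send the reader to Appendix F for the grading scale. Section 8.12 assigns grading to Appendix F and management to Appendix G. SAP Section 3.5.1 allows only the ASTCT grade for CRS. SAP Section 3.5.2, however, says that the criteria for GVHD and CRS are found in Appendices E, F and G together.

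**The concern.** The two appendices are meant to work in sequence: grade the event with F, then read the management from G. That works only if a grade number means the same thing in both. Here it does not, and no sentence maps one set of descriptions onto the other.

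What is at stake is mainly care. The Grade 3 to 4 row of Appendix G is the only one that lists tocilizumab and methylprednisolone. The row chosen can also bear on the study product: Section 1.5.1 reports that donor-derived virus-specific T cells appear not to persist in patients on methylprednisolone at 1 mg/kg/day or more, and the Grade 3 to 4 row specifies 2 mg/kg. If a site took its grade from Appendix G's descriptions, the recorded CRS severity and the second-infusion rule could also be affected.

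**Working it through.** No power, alpha or event-count figure is involved, so the check is a comparison of the two tables.

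| Feature | Appendix F (ASTCT) | Appendix G |
|---|---|---|
| Fever | Same threshold at every grade; its height does not change the grade | Low-grade fever at Grade 1; high fever is enough for Grade 2 |
| Hypotension, no vasopressor | Grade 2 | Grade 2, if mild |
| Hypotension, one vasopressor | Grade 3 | Low-dose vasopressors sit in the Grade 2 management entry |
| Haemodynamic entry to Grade 3 to 4 | Need for a vasopressor | Instability despite fluids and vasopressors |

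**Case 1: fever and hypotension, stable on one low-dose vasopressor, no other criterion met.**
- Appendix F: footnote b states that "hypotension requiring 1 vasopressor, and hypoxia requiring low-flow nasal cannula is classified as grade 3 CRS". Low-flow oxygen alone is a Grade 2 feature, so in that example the vasopressor sets the grade. Case 1 is Grade 3.
- Appendix G: the patient is not unstable despite vasopressors, so does not meet the haemodynamic criterion of the Grade 3 to 4 row. The patient does fit the Grade 2 row.
- Result: the Appendix F number leads to the Grade 3 to 4 row; the Appendix G description leads to the Grade 2 row.

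**Case 2: temperature 39.5°C (taken here as a high fever), no hypotension, no hypoxia.**
- Appendix F: Grade 1.
- Appendix G: Grade 2, because one listed feature suffices.
- Result: one grade apart. The management difference is small, mainly observation with symptomatic support against antipyretics and other measures as needed.

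**Effect on the Section 4.3.2 rule.** It needs Grade 3 or 4 lasting more than 72 hours. Case 2 cannot reach it on either reading (1 or 2). Case 1 can, but only if the vasopressor need outlasts 72 hours before the second infusion, and the two readings part only if a site wrongly grades from Appendix G.

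**Likely frequency.** Appendix G reports 0 CRS cases in 58 participants of the Phase 2 study. The exact two-sided 95% upper limit for 0 of 58 is 1 − 0.025^(1/58) = 0.062, or 6.2%. The planned total is about 125. Even if every randomised participant received the cells, which overstates exposure, that limit gives 125 × 0.062 ≈ 8 cases of any grade. Cases 1 and 2 would be a subset. This assumes that the Phase 2 rate carries over to this population and schedule.

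**The case against.** A reader might infer that the protocol has two competing grading scales, so that CRS severity will be recorded inconsistently across some 90 sites and the second-infusion rule has no fixed meaning. The documents do not support that. Protocol Sections 8, 8.1.4 and 8.12, Appendix F itself, and SAP Sections 2.3.4 and 3.5.1 all point to the Appendix F scale. The natural reading of Section 4.3.2 is therefore the Appendix F grade. CRS severity is also only described, with exact confidence intervals and no hypothesis test.

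Three further points favour the plan. Appendix G is framed as recommendations adapted from CAR-T practice and lets sites use their own treatment protocols, so some variation in care is already accepted. The low-dose vasopressor appears in the management column, not in the Grade 2 description, so a patient might enter as Grade 2, receive a vasopressor and then be regraded under Appendix F. And CRS is expected to be rare.

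The point on recording stands, and it limits the concern. The others do not remove it. Regrading to 3 under Appendix F still leaves a patient who is stable on one vasopressor outside the haemodynamic description of Appendix G's Grade 3 to 4 row. Naming Appendix F as the recording scale does not tell the clinician which Appendix G row applies. Rarity makes it more likely that a site will rely on the printed table. Some room for misreading also remains: Appendix F refers to Appendix G for further details, and SAP Section 3.5.2 cites both for criteria.

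**Conclusion.** The contradiction is in the text and should be corrected. Its main consequence is that a patient stable on one low-dose vasopressor is sent to different management rows by the Appendix F grade and by the Appendix G description, and the rows differ in substance. The high-fever mismatch is real but minor.

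For the tabulated CRS endpoint and the Section 4.3.2 rule, the effect is limited to a possible misreading, because Appendix F is the designated scale. Few participants are likely to be affected. The conclusion rests on the readable text of both tables and footnote b, and on there being no mapping between the two sets of grades in either document. It takes no position on which grade definition or treatment is right.

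**What to change.** Reconcile Appendix G's row descriptions with the Appendix F grades, so that one grade definition governs recording, the Section 4.3.2 rule and the management table. The wording should settle both cases above: hypotension stable on one vasopressor, and high fever alone. Which definition and which management apply is for the sponsor's clinicians to decide.

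In SAP Section 3.5.2, change the cross-reference so that for CRS it names only the grading appendix.

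The cost is a few lines of protocol wording, one line in the SAP and a clarification letter to sites. No change to sample size, data collection or analysis is needed.
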